Because of its simplicity, TRE may represent a more feasible approach for adolescents than other caloric restriction regimens. Our team recently conducted the first study examining the feasibility of TRE in adolescents with obesity. In this study, fifty adolescents were randomized to a self-selected 8-hour TRE compared to a prolonged eating window. TRE was found to be feasible, safe, and acceptable but there was no difference in glycemic profiles or weight loss between groups. These null findings may be due to the late eating window that was selected. To date, there have been no trial comparing early vs. late TRE on glycemic profiles in adolescents and it is unclear how meal-timing impacts glycemic profiles in youth. It remains unknown how the timing of meal consumption directly effects glycemic profiles and cardiometabolic endpoints in this age group. Thus, to address this question, in our proof-of-concept study, we aim to measure glycemic and metabolic responses to a test meal (controlled for macronutrient profile and caloric amount) at various meal-timings (early vs. afternoon vs. late) in thirty Latino adolescents (ages 13-19 years), with obesity, without diabetes. All participants will consume three standard test meals administered in random order at different times of day over a two-week period: (1) Early: test meal consumed at 8 AM; (2) Afternoon: 12 PM; (3) Late: 4 PM. Test meals will be consumed on different days at least three days apart after a minimum of a 16-hour fasting period. A continuous glucose monitor (CGM) will be placed on the participant for the duration of the 2-week period. The **primary endpoints** will be frequently sampled glucose, insulin, and c-peptide area under the curve (AUC) collected after consumption of a standard test meal, insulinogenic index (IGI: change in insulin/change in glucose over the first 30 min after the load), and glucose variability as captured by percent time in range on CGM. We **hypothesize** that adolescents with obesity will have reduced AUC and IGI following the later meals compared to the early meal. We will test these hypotheses with the following aims:

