Aim 1: Identify how timing of meal consumption after a prolonged 16-h fast affects glucose and insulin response in Latino adolescents with obesity. We will measure insulin secretion, clearance rates, and sensitivity assessed with a) 3-h frequent sampling of glucose, insulin, and c-peptide post meal, b) calculated insulinogenic index, and c) percent time in range measured by CGM. *We expect* that meal consumption at 12 and 4 PM will be associated with lower post prandial glucose excursions, decreased AUC and IGI, and increased percent time in range compared to that same meal consumed at 8 AM.

Aim 2: Examine the association between timing of meal consumption and incretin and pancreatic hormones in Latino adolescents with obesity. We will collect frequent sampling of glucagon, total GLP-1, GIP, and PP concentrations post-meal to explore how diurnal variation in these hormones impact insulin sensitivity. **We expect** that meal consumption at 12 and 4 PM will in greater change in incretin and pancreatic hormones concentrations compared to that same meals consumed at 8 AM.

Future Direction: The data collected during this pilot will inform the design of a randomized clinical trial to test the feasibility, safety, and efficacy of early vs. late TRE in adolescents with obesity to reduce glycemic and insulin response for the prevention of type 2 diabetes.

RESEARCH STRATEGY

i. Significance:

In the United States, 1 in 5 adolescents has obesity, and 30-50% of those go on to develop early onset type 2 diabetes. Increased pediatric obesity has been accompanied by a rising incidence of type 2 diabetes in adolescents, specifically among Latino youth. With increasing prevalence and increasing cost for care, obesity in adolescents is expected to result in extensive financial costs, and significant life limiting complications. In adolescents, conventional obesity treatment comprehensively addresses nutritional, physical activity, and behavioral topics with the goal of achieving clinically meaningful weight loss. Adherence to comprehensive lifestyle interventions is challenging for adolescents, in part because these approaches require frequent monitoring and engaging in multiple behavioral targets continuously. Therefore, there is a growing interest in simplifying intervention recommendations to decrease reliance on numeracy (Kilo calories and macronutrients), goal setting and complex skillsets. One simpler and promising approach is based on timing of eating.

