release, and diurnal variation in adolescents with obesity. **Expand our understanding of the use of CGM in adolescents with obesity.** There is very limited experience of the use of CGM among underserved racial/ethnic minority populations at risk for type 2 diabetes. Current CGM-based metrics provide a clinically meaningful macroscopic perspective on an individual's glycemia. This study aimed to gain data-driven insights from the postprandial glucose response to meal consumption at various times throughout the day to determine if changes in glucose peaks shift by the time of first meal consumption. Results from this study could potentially change the way adolescents with obesity are treated in the future by incorporating meal-timing behaviors as part of their medical regimen.

PROCEDURES INVOLVED

Overview of Proposed Study Design: We propose a cross-over, proof-of-concept study to measure glycemic and metabolic responses to a test meal (controlled for macronutrient profile and caloric amount) administered at various times of the day (early vs. afternoon vs. late) in thirty Latino adolescents (ages 13-19 years), with obesity, without diabetes, to determine how timing of eating impacts glycemic response to the test meal after a 16-h fasting period. All participants will consume three standard test meals administered in random order at different times of day over two-weeks: (1) Early: test meal consumed at 8 AM; (2) Afternoon: test meal consumed at 12 PM; (3) Late: test meal consumed at 4 PM. A continuous glucose monitor (CGM) will be placed on the participant for the duration of the 2-week period. Baseline and post-meal samples will be assayed for glucose, insulin, c-peptide, GLP-1, GIP, PP at times -10, , 10, , 30, , 60, 90, 120, and 180 minutes after glucose. The proposed protocol is modified to include multiple samples during the initial 30 minutes when glucose is rapidly increasing, allowing for modeling of glucose stimulated insulin secretion. The primary endpoints will be glucose, insulin, and C-peptide area under the curve, insulinogenic index, and glucose variability as captured by percent time in range on CGM following the test meal.

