Aim 1: Identify how timing of meal consumption after a prolonged 16-h fast affects glucose and insulin response in Latino adolescents with obesity.

Quantifying glycemic profile after test meal from venous sample: Baseline and post-meal samples will be assayed for glucose, insulin, and c-peptide at times -10, , 10, , 30, , 60, 90, 120, and 180 minutes after the meal is consumed. The proposed protocol is modified to include multiple samples during the initial 30 minutes when glucose is rapidly increasing, allowing for modeling of glucose stimulated insulin secretion. Using this approach to model glucose kinetics without the need to administer insulin is a safe and cost-effective surrogate of β -cell function and can be more easily implemented in youth. Insulinogenic index (change in insulin/change in glucose over the first 30 min after the load) will be calculated. IGI has been widely used as an index of early phase insulin secretion in clinical studies. It is highly correlated with the acute insulin response on intravenous glucose tolerance test and is considered a reasonable surrogate.

Quantifying glycemic profile on CGM: Four parameters will be computed from CGM data for each test meal segment: Starting glucose: The glucose value at the start of the meal. Time to peak: The time difference between the start of the meal response and the meal response peak in minutes. Maximum glucose rise: The difference between the glucose levels at the start of the meal and post-meal peak in mg/dL. Glucose incremental area under curve: The positive

area under the post-meal glucose curve after subtracting the glucose value at the start. We will capture glucose readings every 5 minutes and obtain the weekly %TIR over the course of the study.

Aim 2: Examine the association between timing of meal consumption and incretin and pancreatic hormones in Latino adolescents with obesity to explore if the enhanced insulin secretion is secondary to corresponding variations in the release of incretin hormones.⁵¹

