Quantifying incretin hormones after test meal from venous sample: Following baseline sampling (0 min), a test meal will be administered. glucagon, GLP-1, GIP, and PP concentrations will be measured in duplicate from plasma samples using Millipore Enzyme-linked Immunosorbent Assays (ELISA) or multiplex assays according to the recommendations of the manufacturer (Birmingham, MA). Total area under the curve (AUC) will be calculated for venous glucagon, GLP-1, GIP, and PP concentrations using the trapezoid methods using GraphPad Prism (Version .01, GraphPad Software Inc, San Diego, CA, USA).

Statistical Consideration: The sample size estimates, and analytical plans were developed under the guidance of [name] who is the Director of the TSRI Biostatistics core and who will also be a mentor on this award. Descriptive statistics, including graphical depictions, will be utilized to assess the degree of symmetry/normality of continuous outcomes and identification of outliers. A ladder of powers approach will be applied to identify the best easy-to-interpret transformation of the continuous outcome variable. The statistical approach will be implemented with and without transformations when appropriate. Data for this 3-treatment, 3-period cross-over design will be analyzed using linear mixed effects model as described in the literature and implemented in STATA 17.1 (College Station, TX) Sensitivity analysis applying weighted least squares regression will follow. Areas under curves (AUC) will be calculated by the trapezoid rule for levels after meal ingestion. Separate AUC will be calculated for the early (initial 30-min) and the total (entire 300-min) responses. This separation of responses in early and total was decided based on previous findings that insulin secretion is progressively increased during these first 30 min after oral nutrient ingestion. Wilcoxon matched paired test will be used for tests of significance between variables obtained during morning, afternoon, and evening meal ingestion. Spearman regression coefficients will be obtained to estimate correlation.

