Mixed-effects linear regression model was used to assess changes in glucose, insulin, and c-peptide profile over the course of 180 minutes and the difference of first mealtime at 8:00AM, 12:00PM, and 4:00PM univariately. The difference of mealtime over the course of 180 minutes on glucose, insulin and c-peptide levels was assessed by including mealtime as an interaction term in the mixed-effects linear regression model. Due to the skewness of the distribution, differences in glucose, insulin, and c-peptide AUCs over 180 minutes and the insulinogenic index by mealtime were assessed on a logarithmic scale. Profiles that were significantly differ across meal timing were subjected to pairwise comparisons using the false discovery rate based on Simes' method. Changes in profiles were described using beta estimates (β) with its associated 95% confidence intervals and p-values. Pairwise comparisons were presented as percent changes with its associated 95% confidence intervals, unadjusted and adjusted p-values.

The secondary outcome variables included incretin levels and pancreatic hormones, which includes glucagon, pancreatic polypeptide, glucagon-like-peptide-1 (GLP-1), and glucose-dependent-insulinotropic polypeptide (GIP). Mixed-effects linear regression model was used to assess the changes in incretin levels and pancreatic hormones between pre- and post-intervention timepoints. Additionally, mealtime difference on the changes in incretin levels and pancreatic hormones was assessed by including an interaction term in the model, and these variables were analyzed on logarithmic scale. The distributions of incretin levels and pancreatic hormones were described in median and interquartile range by pre- and post- intervention timepoints. The paired difference of pre and post was described using median and 95% confidence intervals by mealtime. Statistical significance was set at 0.05 with two-sided test and all statistical computations were performed in Stata/SE 18.0 (StataCorp, College Station, TX).

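### A mealtime difference in the insulin-based insulinogenic index cannot by itself be attributed to secretion rather than clearance, and no glucose-referenced early C-peptide measure or clearance measure is analysed.

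*Combined protocol and SAP*

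**What the plan says.** The Overview of Proposed Study Design makes IGI primary: "The primary endpoints will be glucose, insulin, and C-peptide area under the curve, insulinogenic index, and glucose variability". The Aim 1 measurement section, on venous samples after the test meal, defines it: "Insulinogenic index (change in insulin/change in glucose over the first 30 min after the load) will be calculated". It goes on to say how the index is to be read: "IGI has been widely used as an index of early phase insulin secretion in clinical studies". Specific Aims states the hypothesis that "adolescents with obesity will have reduced AUC and IGI following the later meals compared to the early meal".

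Aim 1 treats secretion and clearance as distinct: "We will measure insulin secretion, clearance rates, and sensitivity assessed with a) 3-h frequent sampling of glucose, insulin, and c-peptide post meal". C-peptide comes from the same tubes as insulin and glucose: "Baseline and post-meal samples will be assayed for glucose, insulin, and c-peptide at times -10, , 10, , 30", and then on to 180 minutes.

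Two places describe the analysis. Statistical Consideration in the protocol says "Separate AUC will be calculated for the early (initial 30-min) and the total (entire 300-min) responses", without naming analytes. The closing Statistical analysis section says "differences in glucose, insulin, and c-peptide AUCs over 180 minutes and the insulinogenic index by mealtime were assessed on a logarithmic scale". That section also models the glucose, insulin and C-peptide profiles over 180 minutes with a mealtime interaction. It contains no 30-minute AUC, no ratio of C-peptide to glucose, no secretion rate and no clearance measure.

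**The concern.** The insulin concentration at 30 minutes reflects how much insulin was secreted and how much was removed before the sample was drawn. If the fraction reaching the circulation is lower at 12 PM or 4 PM, IGI falls even when early secretion is the same as at 8 AM. A fall is also what the hypothesis predicts. An unexplained drop in IGI would therefore look like confirmation, and the wording of the measurement section invites the reader to call it reduced early secretion.

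C-peptide is secreted with insulin and does not undergo the same hepatic removal, so it could help to tell the two explanations apart at no sampling cost. What is at stake is the interpretation of one primary endpoint. The IGI test remains a valid test of whether the circulating insulin response per unit of glucose rise differs by mealtime.

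**Working it through.** **Reading the definitions together.** The documents give no effect size, SD or power for IGI, so there is no planned figure to reproduce.

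| Item | Early (to 30 min)? | Referenced to glucose? | Uses C-peptide? | In Statistical analysis section? |
|---|---|---|---|---|
| IGI | yes | yes | no | yes |
| C-peptide AUC, 180 min | no | no | yes | yes |
| C-peptide profile by mealtime | includes 10 and 30 min | no | yes | yes |
| 30-min AUC | yes | no | not stated | no |
| Insulin clearance | – | – | not defined | no |

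No row is early, glucose-referenced and based on C-peptide, and the clearance promised in Aim 1 has no formula. The protocol sentence that introduces the 30-minute AUC also gives a 300-minute total, while sampling stops at 180 minutes, so it does not describe the final analysis as it stands.

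**Why IGI cannot separate the two.** Suppose a fraction f of secreted insulin reaches the circulation. Then the change in insulin scales with f, and

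log IGI = log f + log(secretion term) − log(change in glucose).

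A mealtime shift in log f passes unchanged into log IGI, the scale on which it is analysed.

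**Size, single contrast.** Assumptions: secretion and glucose rise identical at both mealtimes; within-participant SD of log IGI s = 0.4; two-sided 0.05. The 0.05 level and n = 30 are from the documents; s and the shift x are assumed. Noncentrality = |ln(1 − x)| / (s√(2/n)), with n − 1 df.

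- Denominator at n = 30: 0.4 × √(2/30) = 0.1033.
- x = 10%: 0.1054 / 0.1033 = 1.02, significant in 17% of trials.
- x = 20%: 0.2231 / 0.1033 = 2.16, significant in 55%.
- n = 22 (75% retention of 30 is 22.5): 13% and 42%.
- s from 0.3 to 0.5 at n = 30: 12–26% for a 10% shift and 39–80% for a 20% shift.

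**Size under the planned testing.** The Statistical analysis section makes pairwise comparisons only after a significant overall difference, with a Simes false discovery rate adjustment; I take this to cover IGI. Simulating three mealtimes with one shifted, n = 30 and s = 0.4, a given contrast is significant in about 10% (10% shift) or 45% (20% shift) of trials. At least one contrast involving the shifted mealtime is significant in about 15% or 56%. With s = 0.8, a 20% shift gives about 11% for a given contrast.

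**If the change is in systemic clearance.** The one-to-one mapping above is for loss before insulin reaches the circulation. In a one-compartment model with an assumed insulin half-life of 4–10 minutes and fixed secretion, 10% higher clearance lowers the 30-minute IGI by only about 4–7%, and 25% higher clearance lowers it by about 10–15%. For the 4–7% fall, a given contrast is significant in about 3–5% of trials under the planned testing. In the same model the corresponding C-peptide index has a ratio of 1.000 throughout, because C-peptide kinetics were held constant.

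**The case against.** The best defence is that C-peptide is far from unused. Its AUC is itself a primary endpoint, its profile is modelled by mealtime with the 10- and 30-minute draws included, and a clearance effect would tend to show as insulin and C-peptide moving apart. The 30-minute AUC is justified in the protocol by early insulin secretion and may well have been meant to include C-peptide. The measurement section calls IGI only a surrogate, and the protocol explains why clamp methods were out of reach in a small proof-of-concept study.

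Most of this stands, and it confines the point to the reading of IGI. It does not close the gap. A 180-minute total is not an early measure, neither the AUC nor the profile is set against the glucose rise, and no rule says how to read IGI if insulin and C-peptide disagree. Nor does the correlation with the intravenous acute insulin response settle it, because that comparator is also an insulin response.

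Three stronger readings are tempting, and the documents support none of them:

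- A reader might infer that an IGI difference would be a false finding about secretion. The documents give no evidence that clearance changes between 8 AM, 12 PM and 4 PM.
- A reader might infer that Aim 2 rests on IGI. The incretin analyses use AUCs and pre/post changes by mealtime, and the planned Spearman correlations name no variables.
- A reader might take 17% and 55% as the plan's error rates. They are single contrasts without the overall test or the adjustment, on an assumed SD and an assumed shift.

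**Conclusion.** The point holds for the interpretation of IGI. The plan presents an insulin-only index as early secretion, names clearance as a separate target, collects the analyte that could help to separate them, and specifies no analysis that does so for the early glucose-referenced response. This follows from the definitions and needs no numbers.

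The practical size is uncertain. About 10% or 45% per contrast applies to a 10% or 20% fall in IGI at s = 0.4 and n = 30. It is lower if SDs are larger, fewer participants complete, or the change is in systemic rather than first-pass clearance. A C-peptide index would be free of this problem only if C-peptide kinetics do not themselves vary by time of day. The point is worth correcting because the remedy is cheap; it does not undermine the trial's other glucose, insulin or C-peptide results.

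**What to change.** In the Aim 1 measurement section and the Statistical analysis section, add two derived variables, each analysed by mealtime in the same log-scale mixed model and labelled as supporting analyses of IGI:

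1. A C-peptide index: change in C-peptide divided by change in glucose, from −10 to 30 minutes.
2. A C-peptide/insulin AUC ratio, as the clearance measure that Aim 1 promises.

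Add an interpretation rule. An IGI difference is attributed to early secretion only if the C-peptide index agrees in direction and size; otherwise it is reported as a difference in circulating insulin response. Say beforehand how agreement in size will be judged, with estimates and 95% confidence intervals side by side. Under this rule the supporting index can only withhold a secretion claim from a significant IGI result and cannot create one, so no claim rests on a test outside the multiplicity adjustment.

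Tie the statement that early sampling allows secretion to be modelled (Overview of Proposed Study Design and the Aim 1 measurement section) to this index. State which analytes the 30-minute AUC covers and whether it is retained.

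Cost: two more variables to report, with no new draws, visits or assays, and the stated assumption about C-peptide kinetics. The Statistical analysis section is written in the past tense; if the analysis has already been run, label both measures as later additions.

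### Post-meal percent time in range is a primary endpoint with a mealtime hypothesis, but its only stated derivation is weekly and the Statistical analysis section names no CGM variable

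*Combined protocol and SAP*

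**What the plan says.** The Specific Aims list among the primary endpoints "glucose variability as captured by percent time in range on CGM", with no time window. The Overview of Proposed Study Design repeats the list and adds the window in words: "glucose variability as captured by percent time in range on CGM following the test meal". Aim 1 attaches a directional hypothesis: the 12 PM and 4 PM meals should give "increased percent time in range compared to that same meal consumed at 8 AM".

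The derivation is in the measurement text for Aim 1, under the paragraph on the CGM glycemic profile. It states "Four parameters will be computed from CGM data for each test meal segment" and lists them: starting glucose, time to peak, maximum rise and incremental AUC. %TIR is not one of the four. It appears in the last sentence of the paragraph: "We will capture glucose readings every 5 minutes and obtain the weekly %TIR over the course of the study". No glucose limits for the range are given anywhere.

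Two other places touch on it. The Schedule of Study Procedures has a time-in-range row marked at Visits 0 to 3, and the CGM paragraph under Study Timelines has a participant report created at each visit. Neither gives a window or a formula.

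On analysis, Statistical Consideration says "Data for this 3-treatment, 3-period cross-over design will be analyzed using linear mixed effects model" and adds a Wilcoxon paired test between mealtimes. It names no CGM variable. The Statistical analysis section after the reference list names the glucose, insulin and c-peptide profiles and their AUCs over 180 minutes, the insulinogenic index, and the incretin and pancreatic hormones. It too names no CGM variable.

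**The concern.** The endpoint, its hypothesis and its derivation refer to different units of time. The endpoint and hypothesis concern the hours after one test meal. The derivation concerns a calendar week in which participants otherwise eat their own uncontrolled meals. If the weekly rule is followed, a named primary endpoint cannot answer the mealtime question set for it.

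If the rule is not followed, the window and the glucose limits remain open and could be chosen after the data are seen. If the closing Statistical analysis section is the full analysis, a primary endpoint has disappeared without a stated reason. The insulinogenic index, listed beside %TIR in the Specific Aims, was carried through to that section; %TIR was not.

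**Working it through.** The documents give no effect size, SD or power for %TIR, so there is no planned figure to reproduce and none is claimed here. The check is arithmetic on the plan's own inputs.

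**Inputs**
- One CGM reading every 5 minutes, i.e. 12 per hour (Aim 1, CGM paragraph).
- Sensor wear of 14 days (Study Timelines).
- Three test meals at least three days apart (Specific Aims), nominally on Days 1, 7 and 14 (Schedule of Study Procedures).
- At least 16 h of fasting before the meal and 3 h without food after it (Study Timelines).

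**Values against conditions.** 14 days / 7 = 2 weekly values per participant, for 3 mealtimes. If all three meals fall within wear, at least two must share a week. Three days out of 14, each at least three days apart, can be chosen in C(14 - 4, 3) = C(10, 3) = 120 ways, and in all 120 some week contains two or more meals. On the nominal schedule, with weeks counted from Day 1, week 1 (Days 1-7) holds two meals and week 2 (Days 8-14) holds one. Week 1 then mixes two mealtimes in every randomised sequence.

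**How much of a week is test meal.** Weekly readings: 12 x 24 x 7 = 2,016. The documents set no %TIR window, so a range is shown.

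| Assumed window | Readings | Share of week |
|---|---|---|
| 3 h after the meal | 3 x 12 = 36 | 36 / 2,016 = 1.8% |
| 300 min (stated for AUC only) | 5 x 12 = 60 | 60 / 2,016 = 3.0% |
| 16 h fast plus 3 h | 19 x 12 = 228 | 228 / 2,016 = 11.3% |

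The third row is an upper bracket, since the fast is not post-meal time. On the 3-h window, a 20-point difference in post-meal %TIR moves the weekly value by 20 x 36 / 2,016 = 0.36 points. The largest possible difference, 100 points, moves it by 1.79 points. One could in principle regress weekly values on which meals fell in which week, but that model would work on a signal diluted to this extent, and the plan describes no such model.

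**What a per-meal derivation gives.** Each participant has three values, one per mealtime. Over 180 minutes each rests on 36 readings and moves in steps of 100 / 36 = 2.8 points.

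**The case against.** The strongest reply is that a per-meal value was plainly intended. The overview scopes the endpoint to the period after the meal, the CGM paragraph already works in test-meal segments, and the schedule marks time in range at each visit. The weekly sentence may be only an added descriptive summary, since the text does not call it the primary derivation. That is a fair reading of intent, but none of these places supplies a window, limits or a formula, and the schedule row is also marked at Visit 0, when no meal is given. The weekly rule is the only one an analyst could follow.

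A second reply is that the closing Statistical analysis section is in the past tense, speaks of the present analysis and cites a different Stata version from Statistical Consideration, so it may be the methods text of a single report. This stands. Whether %TIR was dropped is therefore only moderately certain, but no other analysis section in these documents names a CGM variable.

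A third reply is that the week 1 count depends on starting at Day 1. This is correct. The sensor is placed at Visit 0. If that is one day before Day 1, Day 7 becomes wear day 8 and Day 14 becomes wear day 15, outside wear. Week 1 then holds one meal, but the third mealtime has no CGM data, and a single meal is still 1.8% of its week on the 3-h window. The conclusion does not improve.

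Finally, the four per-meal CGM measures and all the venous endpoints do address mealtime response. That limits the damage but does not supply the missing primary endpoint.

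**Conclusion.** The concern holds, and the plan should be corrected. As derived, weekly %TIR gives two values for three mealtimes and cannot test the Aim 1 prediction. That result needs only the 14-day wear and the three meals. The 1.8% share assumes a 3-h window; most of the weekly value reflects other time on every basis shown. Confidence is high on the mismatch between endpoint, hypothesis and derivation, moderate on whether the endpoint was dropped, and low on how much CGM data the wear period loses, because the gap between Visit 0 and Visit 1 is not stated. The problem is confined to one of several primary endpoints.

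**What to change.** Replace weekly %TIR as the primary derivation with %TIR for each test meal over 0-180 minutes from meal start, the anchor already used for the CGM segments, and state the glucose limits. This window agrees with the "3-h frequent sampling of glucose, insulin, and c-peptide post meal" in Aim 1 and with the 180-minute AUCs in the Statistical analysis section. It conflicts with Statistical Consideration, which says "Separate AUC will be calculated for the early (initial 30-min) and the total (entire 300-min) responses"; the two windows must be reconciled.

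Analyse %TIR by mealtime in the planned crossover mixed model, with the planned Wilcoxon paired test as a check, because the outcome is bounded and moves in 2.8-point steps. Keep weekly %TIR as a descriptive summary. Either add %TIR to the outcome list in the Statistical analysis section, or record when and why it was dropped. It would also help to state a minimum CGM coverage per segment, which segment counts when a visit is repeated, and how %TIR enters the multiplicity procedure.

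A smaller point: 14 days of wear from enrollment is not reconciled with the 7-day window either side of Day 14 or with repeat visits (up to six in total). Reconcile these, or report the number of captured CGM segments by period and mealtime.

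The cost is some re-segmentation of 5-minute data already captured, plus wording, with no new visits. Segments that fell outside sensor wear cannot be recovered. If the CGM data have already been examined, the window and limits must be labelled post hoc, and the endpoint can no longer be presented as pre-specified in this form.
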